The second surgical technique used in the study will be the posterior approach. This approach uses a standard OR table with the patient placed in the lateral decubitus position. A 12-14cm skin incision is utilized over the posterior-lateral corner of the hip. The gluteus maximus muscle is split in line with its fibers and the posterior capsule is opened. The hip is dislocated posteriorly and a femoral neck osteotomy is performed. The acetabular and femoral components are inserted in the same manner as is done with the anterior approach with press-fit fixation utilized. The posterior approach is well described in all major texts on Orthopedic Surgery. To minimize selection bias the surgical technique will be determined by a randomization schedule.

Radiographs and clinical data will be gathered for each qualifying patient in the manner outlined in the Study Procedures below. Harris Hip Evaluation scoring will be used to evaluate pain, function, activity levels, deformity, and range of motion. The HOOS patient reported outcomes will be used to evaluate function and pain relief.

Deaths, device, and procedure related complications will be reported.

Data to be collected includes, but is not limited to that specified in Section 5.2 below.

The primary focus of the study is to compare the short-term safety, efficacy and return to function of patients undergoing primary total hip arthroplasty utilizing an anterior approach vs a posterior approach. Upon completion of the study, a summary of the results will be submitted for publication.

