5.0 Data Collection

5.1 Pre-operative Data Collection

Subject ID
Date of Birth
Gender
Height
Weight
BMI
Left or right hip
Diagnosis

IIS Clinical Research Agreement
[name]
January 28, 2013

Harris Hip Score Elements
Set of x-rays
Pre-op hematocrit and hemoglobin
Timed walking test

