The investigator will offer to answer any questions the Subject may have. If the Subject agrees to participate in the investigation, then the Subject must sign and date the IPC form prior to the day of surgery. However, if the IPC is signed on the day of surgery, then the source document must state that the Subject was given adequate time prior to the time of surgery to review and give consent. In such a case, the time the Subject signed the IPC form must be documented.

The original IPC form remains with the clinical investigator (i.e., within the CRF booklet or clinic chart) and a copy is provided to the Subject. The IPC is not forwarded to the Sponsor. Instead, the Investigator will complete the "Assurance of Investigator" form documenting that informed consent has been properly obtained and then submit a copy to the Sponsor. Once a Subject has executed the IPC documentation, they are considered a study Subject.

Post-operative visit schedule will consist of the following: pre-op, operative, and post-operatively at 2 weeks, 4-6 weeks, 3 months, 6-months, 12-months, 24 months and 60 months.

Time

2 weeks (7-21 days)

Data Collected

Average Pain Score (VAS)

Amount of pain MED use/day

Walking Distance

Use of Assistive Device

IIS Clinical Research Agreement
[name]
January 28, 2013

4-6 weeks (22-45 days)	Average Pain Score (VAS) Average pain MED use/day Walking distance Assistive Device X-ray Protocol cup position stem position limb length offset Return to work/Activity/Driving Timed Walking Test Harris Hip Score HOOS
3 months (60-120 days)	Pain Score (VAS) Average pain MED use/day Walking distance Assisted device Timed Walking Test Harris Hip Score HOOS
6 months (130-240 days)	Average Pain Score (VAS) Harris Hip Score HOOS
12 months (270-425 days)	Average Pain Score (VAS) Harris Hip Score X-ray Protocol HOOS
24 months (426-1460)	Average Pain Score (VAS) Harris Hip Score X-ray Protocol
60 months (1461-2737)	Average Pain Score (VAS) Harris Hip Score X-ray Protocol

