6.0 Statistical **Methodology**

Treatment Assignment

Treatment assignment will be determined with the use of a randomization schedule that will utilize blocks to ensure approximate treatment balance at any time during the study enrollment phase.

Sample Size Determination

Sample size was determined with the use of historical unpublished data of Harris Hip parameters at 6 weeks post-operatively from patients who underwent the primary THA using the anterior surgical approach. The percentage of patients at 6 week post-operative that had the ability to climb stairs normally, and walk unlimited, were 37%, and 40% respectively. Using a 2-tailed Fisher's Exact test and assuming a difference in clinical results of 30% and statistical power of 85% the required sample size for this study is 40 patients per treatment group. To account for 10% attrition the sample size was increased to 44 patients per treatment group (88 patients total).

Primary Endpoint

The proportion of patients with the ability to climb stairs normally or walk unlimited at 6 weeks post-operatively is the primary endpoint in this study. However, the HOOS patient self-assessment dimensions of Pain, Symptoms, Activities of Daily Living, Sport & Recreation, and Quality of Life will be important secondary endpoints. Six minute walk test distances and VAS Pain scores are also secondary endpoints

Analysis Populations

The Intent-to-Treat population will be analyzed.

Interim Analyses

No formal interim analyses will be conducted.

Analyses Planned

Demographics of the 2 treatment groups and pre-operative Harris Hip Evaluation sub-scores and HOOS sub-scores will be compared using appropriate statistical methodologies to determine comparability of treatment groups pre-operatively.

The proportion of patients able to climb stairs normally or walk unlimited as evaluated with the Harris Hip Evaluation at 6 weeks post-operatively will be compared using a 2-tailed Fisher's Exact test. Potentially covariates (e.g. age, BMI, gender) will be assessed using logistic regression techniques.

IIS Clinical Research Agreement
[name]
January 28, 2013

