HOOS sub-scores of Pain, Symptoms, Activities of Daily Living, Sport & Recreation, and Quality of Life will be scored according to the HOOS Users Guide and will be compared using parametric or non-parametric techniques (as appropriate) at 6 weeks, 3, 6 and 12 months post-operatively to determine if there is a difference between treatment groups and at what time points the difference are detected.

Six minute walk test distances at 6 weeks and 3 months and VAS Pain scores will also be compared using parametric or non-parametric techniques (as appropriate) at 6 weeks, 3, 6, 12 months, 24 months and 60 months post-operatively to determine if there is a difference between treatment groups and at what time points the difference are detected.

The prevalence of both inter-operative and post-operative complications and adverse events such as dislocation, hospital re-admission, revision operation, and other postoperative events not normally associated with THA will be compared between groups using a Fisher's Exact (2-tailed) test, with $p \leq 0.05$ being considered significant.

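### The post-operative Harris score is collected at six visits but never compared between approaches, so function has no planned comparison after 12 months; the secondary comparisons also specify no baseline adjustment

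*Combined protocol and SAP*

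**What the plan says.** Section 1.0 sets the objective as a comparison of clinical and functional outcomes over a period of up to 5 years. Section 2.0 gives the Harris score its role: "Harris Hip Evaluation scoring will be used to evaluate pain, function, activity levels, deformity, and range of motion".

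Section 5.1 lists "Harris Hip Score Elements" pre-operatively. The post-operative visit schedule (after Section 5.4) lists the Harris Hip Score at 4-6 weeks and at 3, 6, 12, 24 and 60 months. The entry at both 24 and 60 months reads "Average Pain Score (VAS) Harris Hip Score X-ray Protocol", with no HOOS and no timed walk.

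Section 6.0 uses Harris data twice. Before surgery, "pre-operative Harris Hip Evaluation sub-scores and HOOS sub-scores will be compared using appropriate statistical methodologies to determine comparability of treatment groups pre-operatively". After surgery, the primary endpoint is "The proportion of patients able to climb stairs normally or walk unlimited as evaluated with the Harris Hip Evaluation at 6 weeks post-operatively".

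The planned secondary comparisons are:
- HOOS sub-scores, "compared using parametric or non-parametric techniques (as appropriate) at 6 weeks, 3, 6 and 12 months post-operatively to determine if there is a difference";
- walk distance and pain: "Six minute walk test distances at 6 weeks and 3 months and VAS Pain scores will also be compared using parametric or non-parametric techniques", with VAS continuing to 24 and 60 months;
- complications, by Fisher's exact test, with no stated time limit.

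The covariates named as examples (age, BMI, gender) belong to the logistic regression for the primary endpoint. No pre-operative value is named for any secondary comparison.

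**The concern.** The objective, the visit schedule and the analysis plan do not line up. The Harris score is the only functional score collected at 24 and 60 months, and no analysis is assigned to it. Any later statement about function at 2 or 5 years would be post hoc, with the choice of total or sub-score, visit and method made after the data are known.

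The second, smaller matter is that each secondary outcome is compared on its post-operative value alone. Where a pre-operative value of the same measure exists, leaving it out gives up precision in a trial of about 40 evaluable patients per group.

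**Working it through.** **Which functional measures are collected and compared, by visit** (visit schedule against Section 6.0):

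| Visit | Harris collected | Post-operative Harris score compared | Other functional comparison planned |
|---|---|---|---|
| 4-6 weeks | yes | no (stairs/walking proportion only) | primary proportion, HOOS, walk distance |
| 3 months | yes | no | HOOS, walk distance |
| 6 months | yes | no | HOOS |
| 12 months | yes | no | HOOS |
| 24 months | yes | no | none |
| 60 months | yes | no | none |

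The Harris score or its sub-scores are compared at 0 of 6 post-operative visits, and function by any measure at 0 of the 2 visits after 12 months.

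**Which secondary comparisons could use a baseline:**
- HOOS: 5 sub-scores x 4 visits = 20. A pre-operative HOOS is implied by the comparability check in Section 6.0 but is missing from the list in Section 5.1.
- Walk distance: 2 visits. Section 5.1 lists a timed walking test. The visit schedule uses the same label at 4-6 weeks and 3 months, the two visits where Section 6.0 analyses six-minute distance, so the same test is the natural reading.
- VAS: 6 visits. No pre-operative VAS is documented.

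Harris, the measure with the best-documented baseline, is not among these comparisons.

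**The plan's sample size.** Section 6.0 gives 40 per group, raised to 44 for 10% attrition (40 x 1.10 = 44). Exact Fisher power at 40 per group for 40% against 10% is 85.2%, so the figure reproduces under that reading of the 30% difference. Here 40 serves only as the evaluable number (44 x 0.90 = 39.6).

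**Size of the precision loss.** Adjusting for a baseline with correlation r to the outcome multiplies the variance by about 1 - r². The documents give no r, so it is assumed. The unadjusted 95% CI half-width in SD units is t(0.975, 78) x sqrt(2/40) = 1.991 x 0.2236 = 0.445, and the adjusted half-width is that times sqrt(1 - r²). Power is for a 0.5 SD difference, two-sided 0.05, noncentral t.

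| r (assumed) | 1 - r² | 40 per group acts like | Half-width (SD) | Power |
|---|---|---|---|---|
| none | 1 | 40 | 0.445 | 59.8% |
| 0.1 | 0.99 | 40.4 | 0.443 | 60.2% |
| 0.3 | 0.91 | 44.0 | 0.425 | 63.9% |
| 0.6 | 0.64 | 62.5 | 0.356 | 78.8% |

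These use the simple 1 - r² factor. Allowing for estimation of the baseline slope lowers power slightly (63.3% at 0.3, 78.3% at 0.6) and removes the gain at 0.1 (59.7%).

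**Late visits.** If 30 per group remained at 60 months (an assumption), the half-width would be about 0.52 SD unadjusted and 0.49 to 0.41 SD adjusted at r = 0.3 to 0.6.

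**Visit windows.** The 24-month window is 426-1460 days, a span of 1034 days. The 60-month window is 1461-2737 days, a span of 1276 days. At 30.44 days per month these run from about 14 to 48 months and from about 48 to 90 months.

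**The case against.** The strongest reply is that every declared endpoint has an analysis. Section 6.0 names the primary proportion, HOOS, six-minute walk and VAS, and the Harris score is not on that list. Section 2.0 also puts the primary focus on the short term. This stands in part: no declared endpoint lacks an analysis. The gap is between an objective that reaches 5 years, together with the evaluative role given to the Harris score, and an endpoint list that omits it.

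On adjustment, unadjusted comparisons are valid in a randomised trial, and the open wording about parametric or non-parametric methods does not exclude a baseline-adjusted model. Both points stand. The charge is only that no adjustment is specified, and its benefit depends on a correlation the documents do not give.

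A reader might infer more than the text supports:
- *That Section 6.0 ignores the Harris score.* It compares pre-operative sub-scores and builds the primary endpoint from Harris stairs and walking items.
- *That the functional objective has no planned comparison at all.* The primary proportion, walk distance and HOOS cover function up to 12 months.
- *That late follow-up goes unanalysed.* VAS is compared at 24 and 60 months, and the complications comparison has no time limit.
- *That all the secondary comparisons discard an available baseline.* VAS has none documented, and HOOS has one only by implication.

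**Conclusion.** The point holds in limited form. Section 6.0 plans no between-group comparison of the post-operative Harris score or sub-scores at any of the six visits where the score is collected, and function has no planned comparison at 24 or 60 months. This rests on the text alone and needs no assumption.

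The missing baseline adjustment is secondary and affects precision only. At 40 per group, power for 0.5 SD would rise from 60% to 64-79% if the baseline correlation were 0.3-0.6, and hardly at all at 0.1. The gain applies only where a pre-operative value exists: Harris, walk distance if the test is the same, and HOOS if it is collected as Section 6.0 presupposes.

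The primary test is unaffected and no formal claim rests on a secondary result. The plan should be changed, but the trial's main conclusion does not depend on it.

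**What to change.** 1. **Harris score (the priority).** Add between-group estimates with 95% CIs for the Harris total and its pain and function sub-scores at 6 weeks and 3, 6, 12, 24 and 60 months. The sub-scores matter because the total mixes function with pain, deformity and motion. Use a repeated-measures model with treatment, visit and treatment x visit, adjusted for the pre-operative Harris value, and report the results as descriptive secondary estimates. Because the two late windows are wide, report the actual follow-up time by group.

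2. **Baseline adjustment elsewhere.** Analyse walk distance adjusted for the pre-operative timed walking test, after confirming that it is the six-minute test. Analyse each HOOS sub-score adjusted for its own pre-operative value, after reconciling Section 5.1, which omits HOOS, with Section 6.0, which compares it pre-operatively. Leave VAS unadjusted unless a pre-operative VAS turns out to be collected.

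**Cost.** SAP wording, slightly more analysis, and descriptive Harris estimates at six more visits to report. Harris needs no new data. If pre-operative HOOS was not collected, its 20 comparisons gain nothing from item 2.

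### Twenty-eight secondary comparisons are to show whether and when the approaches differ, with no error control and no exploratory label; the chance of at least one false detection is about 25% to 76%

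*Combined protocol and SAP*

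**What the plan says.** All references are to section 6.0, Statistical Methodology, of the combined protocol and SAP.

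- Under Primary Endpoint, one binary outcome at 6 weeks is primary. The five HOOS dimensions "will be important secondary endpoints", and "Six minute walk test distances and VAS Pain scores are also secondary endpoints".
- Under Analyses Planned, the "HOOS sub-scores of Pain, Symptoms, Activities of Daily Living, Sport & Recreation, and Quality of Life" are compared "at 6 weeks, 3, 6 and 12 months post-operatively to determine if there is a difference between treatment groups".
- The next paragraph adds "Six minute walk test distances at 6 weeks and 3 months", and VAS pain "at 6 weeks, 3, 6, 12 months, 24 months and 60 months post-operatively".
- Both paragraphs end with the same purpose: "to determine if there is a difference between treatment groups and at what time points the difference are detected".
- The method is parametric or non-parametric, whichever is appropriate. No longitudinal model or overall test is named.
- A significance threshold (p ≤ 0.05) appears only in the sentence on complications and adverse events.

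The section contains no multiplicity adjustment, hierarchy, key secondary endpoint or key visit. It does not make the secondary claims depend on the primary result, and it does not label them exploratory.

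**The concern.** The stated purpose works as a decision rule. Each endpoint-by-visit comparison can produce a statement that the groups differ and that the difference appeared at that visit. With 28 such opportunities and no limit on the overall error, the rule will produce false statements of this kind much more often than 5% of the time when the approaches are equivalent.

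What is at stake is the published conclusion. Section 2.0 (Overview) says the results will be submitted for publication. If the primary comparison is not significant, nothing in the plan stops a nominally significant sub-score at one visit from being presented as a detected difference. Correlation adds a second problem: chance findings on related scales and neighbouring visits tend to occur together, so they can look like mutual confirmation.

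**Working it through.** **The plan's own figures.** The plan gives no test count and no error rate for the secondary endpoints, so there is no secondary figure to reproduce. The only calculated figure is the primary sample size. Taking 40% against 10% and assuming two-sided alpha 0.05, exact Fisher power at 40 per group is 0.852, and 40 is the smallest size that reaches 85%. That figure covers the one primary test and does not enter the calculation below.

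**Step 1: count the comparisons (Analyses Planned).**

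- HOOS: 5 sub-scores × 4 visits = 20
- Six-minute walk: 2 visits = 2
- VAS pain: 6 visits = 6
- Total: 20 + 2 + 6 = 28

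**Step 2: expected false detections.** Assume no true difference and each test at two-sided 0.05. The expected number is 28 × 0.05 = 1.4, whatever the correlation.

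**Step 3: chance of at least one.** Under independence it is 1 − 0.95^28 = 0.762. The same patients supply all 28 results, so positive correlation is to be expected, but the documents give no value. The range below comes from simulating 28 null z-statistics with a common correlation r (200,000 draws per row; the r = 0 row is the exact figure for the chance). The last column is the mean number of false detections in trials that have at least one.

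| r | P(at least one) | Mean number, given at least one |
|---|---|---|
| 0 | 76% | 1.8 |
| 0.3 | 64% | 2.2 |
| 0.5 | 49% | 2.9 |
| 0.7 | 33% | 4.2 |
| 0.8 | 25% | 5.6 |
| 0.9 | 17% | 8.3 |

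Separate between-endpoint and between-visit correlations, multiplied together, give similar results: 65% (0.3 and 0.5), 58% (0.5 and 0.5), 41% (0.7 and 0.7) and 31% (0.8 and 0.8).

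**Step 4: check candidate remedies.** There are seven endpoints: five HOOS sub-scores, walk and VAS.

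- *Seven 6-week tests, unadjusted.* 1 − 0.95^7 = 0.302 if independent, so restricting attention to 6 weeks is not enough without adjustment.
- *Holm over the seven 6-week tests, later visits exploratory.* Family-wise error is at most 5% under any correlation. The smallest p-value must be at or below 0.05/7 = 0.0071.
- *Holm at 6 weeks, then each endpoint's later visits tested at the level at which that endpoint passed.* This is not valid. Holm has already handed that alpha to the remaining endpoints, so it is spent twice. Suppose all seven 6-week effects are real and large but gone by 3 months. The 3-month tests then run at 0.05/7, 0.05/6, …, 0.05/1, and the error is 1 − ∏(1 − 0.05/k), k = 1 to 7, which is 1 − 0.877 = 12.3% if independent. Simulation gives 11.6%, 10.1% and 8.2% at between-endpoint correlations of 0.3, 0.5 and 0.7.
- *A fixed 0.0071 per endpoint, visits tested in fixed order at that level.* In the same scenario the error is at most 7 × 0.05/7 = 5%.

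**The case against.** The strongest defence is that the plan names one primary endpoint with one prespecified test and calls everything else secondary. Unadjusted secondary tests are common and defensible when they are read as exploratory. This stands in part: the primary error rate is not touched. But the plan does not attach an exploratory label, and it gives these comparisons the task of determining whether and when a difference exists.

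It can also be said that the wording on methods does not strictly exclude a longitudinal model. That is true, but none is specified, and separate comparisons at each visit are the natural reading.

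Three stronger readings are tempting, and the documents do not support them.

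- *A false detection is more likely than not.* This needs a 0.05 level, which the plan states only for complications, and low to moderate correlation. At a common correlation of about 0.5 the chance is already near one half, and it falls below that as correlation rises.
- *The 28 tests decide whether the approaches differ.* They do not do so alone, because the primary comparison is separate.
- *A null trial would probably be published with several chance findings.* The average is 1.4 and the chance of any may be below one half. The larger counts in the table apply only to trials that already have one.

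The complication comparisons are not counted here. They add further opportunities for a false claim, but the plan lists them by example, so their number cannot be fixed.

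**Conclusion.** The concern holds in a limited form. The count of 28 and the absence of any error control or exploratory label come directly from section 6.0. If each comparison is tested at two-sided 0.05 and there is no true difference, 1.4 false detections are expected, and the chance of at least one lies between about 25% and 76% for common correlations from 0.8 down to 0. Even at 0.9 it is 17%, so it exceeds 5% in every case computed. The size rests on two assumptions that the documents do not settle: the 0.05 level and the correlation. The direction does not depend on the correlation assumed.

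This does not invalidate the primary analysis. It should be corrected before the data are analysed because it governs what may be claimed from the secondary results.

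**What to change.** **Main change.** Keep all 28 comparisons. Report each as a between-group difference with a 95% confidence interval, labelled exploratory. Replace the purpose sentence in both paragraphs with one saying that these results describe the size and time course of any difference, and that no secondary p-value will be used to claim one.

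**If the sponsor wants confirmatory secondary claims,** choose one of these in advance and leave everything outside it exploratory:

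1. Test the seven 6-week comparisons with Holm at two-sided 5%, with all later visits exploratory.
2. Give each of the seven endpoints a fixed 0.05/7 = 0.0071. Test its visits in time order at that level and stop at the first non-significant one. Pass its alpha to other endpoints only after its whole sequence has been rejected.

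Do not combine Holm at 6 weeks with later-visit tests at the Holm step level, which can give about 12% family-wise error. State the significance level in whichever option is used.

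**Cost.** SAP wording only, with no extra patients or data. There will be fewer nominal significance claims. Under option 1 an effect that first appears after 6 weeks cannot be claimed. Under option 2 it cannot be claimed for an endpoint that fails at 6 weeks. That matters because section 1.0 sets the objective over follow-up of up to 5 years, so the sponsor should make the choice knowingly.

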5.3 Post-operative Data

Pain scores pre and post administration of pain meds
Amount of pain medication required
Blood loss from drains over 36 hours post op
Hemoglobin / hematocrit on POD # 1&2
Functional activities (distance walked, transfers and assistive devices used)
Length of hospital stay
Harris Hip Score Elements
HOOS
Timed walking tests
Complications/Patient Withdrawal/Revision/Deaths (as applicable)

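### Six-minute-walk distance is compared with no pre-operative term, although a timed walking test is collected before surgery: precision is lost on a secondary endpoint

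*Combined protocol and SAP*

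**What the plan says.** Section 6.0 (Primary Endpoint) gives the walk test its status: "Six minute walk test distances and VAS Pain scores are also secondary endpoints". Analyses Planned then states: "Six minute walk test distances at 6 weeks and 3 months and VAS Pain scores will also be compared using parametric or non-parametric techniques", leaving the choice between the two families to what is appropriate. It names no covariate, change score or other pre-operative term.

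Section 5.1 lists "Timed walking test" among the pre-operative data, and section 5.3 lists "Timed walking tests" after surgery. Pre-operative Harris Hip and HOOS sub-scores have one stated use, a check that the groups are comparable. The pre-operative walking test has no stated use.

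The documents use two names. Data collection speaks of a timed walking test, the analysis section of a six-minute walk, and nothing equates them. In the visit schedule the timed walking test appears in the 4-6 week row ("Return to work/Activity/Driving Timed Walking Test Harris Hip Score HOOS") and the 3-month row ("Walking distance Assisted device Timed Walking Test Harris Hip Score HOOS"), and is gone by 6 months ("Average Pain Score (VAS) Harris Hip Score HOOS").

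**The concern.** How far a patient walks after hip replacement probably depends in part on how far that patient walked before it. A comparison that ignores the earlier measurement leaves this between-patient variation in the error term.

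The trial is sized for a 30-point difference in a binary primary endpoint, so nothing guarantees adequate power for walk distance. With about 40 evaluable patients per arm, a baseline that is already collected is the cheapest source of extra precision. Return to function is part of the study's stated focus in section 2.0, so a real difference in walking should not be missed for want of one covariate.

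**Working it through.** **1. The plan's own figure.** Two-sided Fisher's exact test, 40% v 10%, alpha 0.05 (assumed; the plan states 0.05 only for complications): exact power at 40 per group is 85.2%, and 40 is the smallest number that reaches 85%. The stated sample size reproduces under this reading. The allowance for attrition is 40 × 1.10 = 44. I therefore use 40 evaluable patients per arm, 80 in all.

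**2. Are the two tests the same?** The timed walking test is scheduled after discharge only at 4-6 weeks and 3 months. Those are the two times at which the six-minute walk is analysed. Walking distance is a separate schedule item, also recorded at 2 weeks. The match suggests one test under two names, but does not prove it.

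**3. Normal data.** Assumptions: true difference 0.5 SD, two-sided alpha 0.05, pre/post correlation r.

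- t test: noncentrality 0.5 / √(2/40) = 2.236 on 78 degrees of freedom, giving power 59.8%.
- ANCOVA: the variance is multiplied by (1 − r²)(1 + 1/76). The second term is the price of estimating the slope with 80 patients. Noncentrality is 0.5 / √(factor × 2/40) on 77 degrees of freedom.
- Example, r = 0.5: 0.75 × 1.0132 = 0.760; 0.5 / √(0.760 × 0.05) = 2.565; power 71.7%.

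| r | variance factor | net variance reduction | power | difference detectable at 80% power | equivalent N (80 / factor) |
|---|---|---|---|---|---|
| t test | 1 | – | 59.8% | 0.634 SD | 80 |
| 0 | 1.013 | −1.3% | 59.2% | 0.639 SD | 79 |
| 0.2 | 0.973 | 2.7% | 61.0% | 0.626 SD | 82 |
| 0.3 | 0.922 | 7.8% | 63.3% | 0.609 SD | 87 |
| 0.5 | 0.760 | 24.0% | 71.7% | 0.553 SD | 105 |
| 0.7 | 0.517 | 48.3% | 86.7% | 0.456 SD | 155 |

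ANCOVA breaks even with the t test at r = 0.115.

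**4. Strongly skewed data.** Simulation: lognormal distances, log-SD 0.5, the same 0.5 SD shift, 80 patients, r on the log scale.

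| r | Wilcoxon | plain ANCOVA | ANCOVA on ranks |
|---|---|---|---|
| 0.3 | about 77% | 65% | about 81% |
| 0.5 | about 77% | 72% | about 86% |
| 0.7 | about 77% | 85% | about 95% |

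Plain ANCOVA can lose to the rank test that the plan already permits; ANCOVA on ranks does not at these correlations. Under the null, both forms of ANCOVA rejected in 4.6% to 5.4% of simulated trials.

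**The case against.** **The plan does not forbid adjustment.** Parametric techniques could include ANCOVA. That is true, and this is a gap in specification rather than a wrong analysis. But an adjustment that is not written down is not pre-specified, and the pre-operative walking test is given no role anywhere.

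**The baseline may not be the same test.** This stands, and it limits the point most. If the tests differ and the correlation is only about 0.2, power on normal data is 61% against 60%, which is of no practical value. Confirming the name must come first.

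**The gain is assumed.** This also stands. The documents support no particular correlation, and at 0.3 the gain on normal data is only 63.3 − 59.8 = 3.5 points. The recommendation rests on the asymmetry: about half a point lost at worst on normal data, 12 gained at r = 0.5.

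**Switching by observed skewness.** One might choose the rank version only when pooled pre-operative skewness exceeds 1. In the skewed scenario this triggers in about 78% of trials and gives 75%, 78%, 83% and 93% at r = 0.2, 0.3, 0.5 and 0.7. Wilcoxon gives about 76-77%, and ANCOVA on ranks throughout 79%, 81%, 86% and 95%. The switch should not be used.

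**Stronger readings.** A reader might infer that the planned comparison is biased; it is not, because the arms are randomised. A reader might also fault the primary analysis because the logistic model names no pre-operative function score, although "Harris Hip Score Elements" are collected before surgery. The covariates there are only examples, the Fisher test would not change, and the likely gain is small (about 0.5 to 3 points for a covariate odds ratio of 1.5 to 2 per SD, itself assumed). I do not press that.

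**Conclusion.** The point holds for walk distance alone. An available pre-operative measurement is left out of the analysis of a named secondary endpoint. The unadjusted comparison is valid but probably less precise than it need be.

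The size depends on three assumptions: that the timed walking test is the six-minute walk, that the pre/post correlation is well above 0.12, and that a difference of 0.5 SD is a fair benchmark. At correlations of 0.3 to 0.7 the gain is about 3 to 27 power points on normal data, and about 4 to 18 points over the Wilcoxon test on strongly skewed data. The change is worth making but is not critical.

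VAS pain is outside the point because section 5.1 lists no pre-operative VAS. HOOS is less clear: section 5.1 does not list it before surgery, yet section 6.0 plans to compare pre-operative HOOS sub-scores. If it is in fact collected, the same adjustment applies.

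**What to change.** 1. State whether the timed walking test in sections 5.1 and 5.3 and the visit schedule is the six-minute walk of section 6.0, and use one name throughout.
2. If it is, compare walk distance at 6 weeks and at 3 months by ANCOVA on the pre-operative distance. Where a rank test would have been used, apply ANCOVA to the ranks of the outcome and of the baseline.
3. Name the parametric or the rank version before anyone sees outcome data by arm, with no data-driven skewness threshold.
4. Fill a missing pre-operative value with the pooled mean of both arms, so that no patient is lost from the analysis for lack of a baseline.
5. If the tests differ, use the pre-operative timed-walk result as the covariate and expect little gain.

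The cost is a few sentences in the analysis section. No visit, patient or measurement is added. The statistical downside is about 0.6 power points on normal data if the baseline proves uninformative.
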